10.6. Appendix 6: Hepatitis B Testing Algorithm and Full Eligibility Criteria

For participants in countries in which hepatitis B prevalence has been reported at a rate of >5.0%^a or if required by local standard of care, participants will be tested as follows:

1. At screening, HsBsAg and HBcAB will be tested:
 - a. If both tests are negative, the participant is eligible for study inclusion.
 - b. If HBsAg is positive, the participant must be excluded from participation in the study.
 - c. If HBsAg is negative and HBcAb is positive, HBsAb and HBVDNA reflex testing is required:
 - i. If HBsAb is negative, the participant must be excluded from participation in the study;
 - ii. If HBVDNA is detected, the participant must be excluded from participation in the study;
 - iii. If HBsAb is positive and HBVDNA is undetectable, the participant is eligible for study inclusion. If the subject is included in the study, for subsequent visits HBVDNA testing must be performed according to the SoA ([Section 1.3](#)).

For participants in all other countries, participants will be tested as follows:

2. At screening, HBsAg and HBcAb will be tested:
 - a. If both tests are negative, the participant is eligible for study inclusion.
 - b. If HBsAg is positive, the participant must be excluded from participation in the study.
 - c. If HBsAg is negative and HBcAb is positive, HBsAb reflex testing is required:
 - i. If HBsAb is negative, the participant must be excluded from participation in the study;
 - ii. If HBsAb is positive, the participant is eligible for study inclusion. If the participant is included in the study, for subsequent visits no hepatitis B testing is required.

^a Razavi-Shearer D, Gamkrelidze I, Nguyen MH, et al. Global prevalence, treatment, and prevention of hepatitis B virus infection in 2016: a modelling study. *Lancet Gastroenterol Hepatol* 2018; 3(6):383-403.

10.7. Appendix 7: Guidelines for Participant Safety Monitoring and Discontinuations

These guidelines for participant safety monitoring and discontinuation are to be applied to all participants in Study B7981037. Additional individual participant monitoring is at the discretion of the investigator and dependent on any perceived safety concerns. Unscheduled clinical labs may be obtained at any time during the study to assess such concerns, and a participant may be withdrawn at any time at the discretion of the investigator.

For the purposes of safety monitoring and discontinuation, baseline values will be defined as follows:

- Baseline values will be defined as the most recent pre-dose values before dosing on Day 1 for all participants.

10.7.1. Monitoring

All potential treatment-related events of rash will be followed up until resolution or agreement with Pfizer.

The following laboratory abnormalities require re-testing until resolution or agreement with Pfizer:

Table 3. Laboratory Retesting Criteria

Laboratory Variable	Laboratory Value	Re-testing Timeframe ^a
Hematology		
Absolute Neutrophil Count	<1000/mm ³ (<1.0 × 10 ⁹ /L)	Within 1 week
Hemoglobin	<10.0 g/dL (<6.21 mmol/L or <100 g/L)	Within 1 week
Platelet count	<100,000/mm ³ (<100 × 10 ⁹ /L)	Within 1 week
Absolute Lymphocyte Count ^b	<600/mm ³ (<0.6 × 10 ⁹ /L)	Within 1 week
Serum Chemistry		
Creatine kinase ^c	>3 × ULN	Within 1 week
Aspartate aminotransferase	See Section 10.5 for potential cases of drug-induced liver injury.	Within 48 hours
Alanine aminotransferase	See Section 10.5 for potential cases of drug-induced liver injury.	Within 48 hours
Total bilirubin	See Section 10.5 for potential cases of drug-induced liver injury.	Within 48 hours

a. Based on awareness of the abnormal result.

b. Participants with absolute lymphocyte count <500/mm³ (0.5 × 10⁹/L) will be reflex-tested for FACS-TBNK until the absolute lymphocyte count resolves or stabilizes at a level acceptable to the investigator and sponsor.

c. In addition to re-testing creatine kinase >3× ULN, urine myoglobin will be performed as reflex testing for any participant with creatine kinase >10× ULN for visits on or before Month 15E. For participants who have completed the Month 15E Visit, creatine kinase and urine myoglobin will not be tested.

In case of positive urine pregnancy test, the participant will have study intervention interrupted and a serum sample collected on the same day (or as soon as possible) and submitted to the central laboratory for pregnancy testing.

10.7.2. Discontinuation

Treatment will be discontinued, and the participant withdrawn from this study following completion of the Early Termination visit and the Follow-up Visit (whenever possible) for:

Adverse Events:

- Serious infections, defined as any infection (viral, bacterial, and fungal) requiring parenteral antimicrobial therapy or hospitalization for treatment or meeting other criteria that require the infection to be classified as serious adverse event;
- Treatment-related SAEs;
- Clinically meaningful, treatment-emergent declines in hearing or clinically meaningful, treatment-emergent changes in audiological assessments from baseline (refer to Audiometry Study Guide for details) are to be discussed with the sponsor for possible withdrawal from study;
- Other serious or severe AEs, at the discretion of the investigator or sponsor.

ECG Findings (up to Month 15E Visit):

- Confirmed QT_{cF} >500 ms;
- Confirmed increase from baseline in QT_{cF} of >60 ms.

Study Intervention Interruptions:

- Participants interrupting study intervention for more than 14 consecutive days are to be discussed with the sponsor for possible withdrawal from the study.

Laboratory Abnormalities:

All the following laboratory abnormalities **require discontinuation** if they are confirmed by re-test. Refer to the re-testing timeframes for laboratory abnormalities in [Section 10.7.1](#):

- Absolute Neutrophil Count <750/mm³ (<0.75 × 10⁹/L).
- Hemoglobin <9.0 g/dL (<5.59 mmol/L or <90 g/L) or a decrease of >30% from baseline (either criterion or both).
- Platelet count <75,000/mm³ (<75.0 × 10⁹/L).

- Absolute Lymphocyte Count $<500/\text{mm}^3$ ($<0.5 \times 10^9/\text{L}$).

NOTE: Participants with absolute lymphocyte count $<500/\text{mm}^3$ ($0.5 \times 10^9/\text{L}$) will be reflex tested for FACS-TBNK until the absolute lymphocyte count resolves or stabilizes at a level acceptable to the investigator and sponsor.

- Creatine kinase $>10 \times$ ULN (for visits on or before Month 15E).

NOTE: In addition to re-testing creatine kinase $>3 \times$ ULN, urine myoglobin will be performed as reflex testing for any participant with creatine kinase $>10 \times$ ULN for visits on or before Month 15E. For participants who have completed the Month 15E visit, creatine kinase and urine myoglobin will not be tested.

- Aspartate aminotransferase (AST) or alanine aminotransferase (ALT) that meet ANY of the following:
 - $>3 \times$ ULN with at least one total bilirubin value $>2 \times$ ULN;
 - $>3 \times$ ULN accompanied by signs or symptoms consistent with hepatic injury (eg, new onset elevated PT/INR);
 - Two sequential AST or ALT elevations $>5 \times$ ULN, regardless of total bilirubin or accompanying signs or symptoms.

NOTE: In each case, there is a need for additional investigations, such as review of ethanol, recreational drug, and dietary supplement consumption; testing for acute hepatitis A, B or C infection and biliary tract imaging should be promptly discussed with the sponsor or designee.

Pregnancy:

Female participants confirmed as pregnant during the study (see [Section 8.3.5](#)).

Prohibited Medications:

- Participants who are treated with any prohibited medication during the course of the study may require discontinuation. Participants who are administered a prohibited medication should be discussed with the sponsor for possible withdrawal from the study.

Suicidal Ideation:

- Participants with suicidal ideation associated with actual intent and a method or plan in the past year: a “yes” answer on items 4, 5, or on any question in the suicidal behavior section of the C-SSRS must be discontinued. The participant must be

referred to a mental health professional for appropriate evaluation and treatment or immediately referred to the Emergency Room at the investigator's judgement.

Discontinuation/End of Treatment Monitoring:

- Any participant meeting discontinuation criteria must enter into the Follow-up Period with their first follow-up visit occurring 1 week after their last dose whenever possible, until the event has returned to normal or baseline levels or is deemed clinically stable. The procedures scheduled for Early Termination Visit will be performed on the last day the participant takes the study intervention or as soon as possible thereafter. The only exception to this is when a participant specifically withdraws consent for any further contact with him or her or persons previously authorized by the participant to provide this information. Additional follow-up visits may occur as needed until any clinically relevant abnormalities or adverse events have resolved, returned to a baseline state, or are deemed clinically stable.
- Any participant that is discontinued from study intervention due to an auditory adverse event must have BAEP and auditory assessments performed at the time of discontinuation and repeated at 6 months after the last dose of study intervention. Refer to the Manual for BAEP Evaluations and the Audiology Study Guide for additional information.
- Any participant that is discontinued from study intervention due to a neurological adverse event must have skin biopsy and neurological evaluations, including the Neuropathy Assessment, performed at the time of discontinuation, and repeated at 6 months after the last dose of study intervention. Refer to the Manuals for General Neurological and Neuropathy Assessments for additional information.

10.8. Appendix 8: Prohibited and Permitted Concomitant CYP3A Inducers and Substrates

Please note that this list addresses only CYP3A inducers and sensitive and moderate sensitive CYP3A substrates. Other prohibited medications for this trial are listed in Section 5.2. Refer to Section 6.5.1 for additional information regarding permitted medications for this trial, including CYP3A inhibitors.

This is not an all-inclusive list. Study personnel should stay current and consult with their pharmacy to exclude all concomitant medications that are moderate to potent CYP3A inducers. If a medication is a sensitive or moderate sensitive CYP3A substrate and is not listed here, consultation with the Sponsor is required.

10.8.1. Prohibited Concomitant CYP3A Inducers and Substrates

Sensitive CYP3A Substrates ^a	Moderate Sensitive CYP3A Substrates ^b	Moderate to Potent CYP3A Inducers ^c
Dasatinib	Aprepitant	Avasimibe ^d
Dronedarone	Eliglustat	Bosentan
Ebastine	Pimozide	Barbiturates
Lomitapide	Rilpivirine	Carbamazepine ^d
Nisoldipine		Efavirenz
Sirolimus		Etravirine
Tacrolimus		Mitotane ^d
Tolvaptan		Modafinil
		Nafcillin
		Phenobarbital ^d
		Phenytoin ^d
		Rifabutin ^d
		Rifampin ^d
		St. John's Wort ^d
		Talviraline

a. Sensitive CYP3A substrates are drugs that demonstrate an increase in concentration-time curve (AUC) of ≥ 5 -fold with strong index inhibitors of a given metabolic pathway in clinical drug-drug interaction (DDI) studies.

b. Moderate sensitive substrates are drugs that demonstrate an increase in AUC of ≥ 2 to < 5 -fold. In a situation where appropriate medical care of a participant requires the use of a prohibited CYP3A inducer: Moderate to potent inducers of CYP3A are not permitted in the study EXCEPT in emergency situations. Note: Mitotane is not permitted for any duration due to its long half-life; however, if necessary mitotane may be used in an emergency, however the participant will then be discontinued from the study. Topical (including skin or mucous membranes) application of antimicrobial and antifungal medications is permitted.

c. All prohibited drugs that are CYP3A inducers require at least a 28 day or 5 half-lives (whichever is longer) washout prior to the first dose of study intervention.

d. Notated as potent inducers.

10.8.2. Permitted Concomitant CYP3A Substrates

Sensitive CYP3A Substrates ^a		Moderate Sensitive CYP3A Substrates ^b
Alfentanil	Midazolam	Alprazolam
Avanafil	Naloxegol	Atorvastatin
Buspirone	Quetiapine	Colchicine
Darifenacin	Sildenafil	Rivaroxaban
Eletriptan	Simvastatin	Tadalafil
Eplerenone	Ticagrelor	
Felodipine	Triazolam	
Lovastatin	Vardenafil	
Lurasidone		

a. Sensitive CYP3A substrates are drugs that demonstrate an increase in concentration-time curve (AUC) of ≥ 5 -fold with strong index inhibitors of a given metabolic pathway in clinical drug-drug interaction (DDI) studies.

b. Moderate sensitive substrates are drugs that demonstrate an increase in AUC of ≥ 2 to < 5 -fold.

10.9. Appendix 9: Alternative Measures During Public Emergencies

The alternative study measures described in this section are to be followed during public emergencies, including the coronavirus disease-2019 (COVID-19) pandemic. This appendix applies for the duration of the COVID-19 pandemic globally and will become effective for other public emergencies only upon written notification from Pfizer. NOTE: Any deviations from the SoA (Section 1.3) or the protocol (eg, missed or partially completed procedures or assessments) must be reported to the Sponsor in a timely manner and will be reported by the Sponsor as a protocol deviation.

Procedures which are missed due to disruptions related to a public emergency, including the COVID-19 pandemic, are required to be performed at the next available opportunity, even if outside of a protocol-specified visit window.

Use of these alternative study measures are expected to cease upon the return of business as usual circumstances (including the lifting of any quarantines and travel bans/advisories).

In this appendix, safety assessment terms include 1) special safety assessments (audiological evaluations, including BAEP, by the audiologist, neurological evaluation by the neurologist, and the skin biopsy) and 2) usual safety assessments (all other safety evaluations).

10.9.1. Eligibility

While severe acute respiratory syndrome coronavirus 2 (SARS-CoV-2) testing is not mandated for this study, local clinical practice standards for testing should be followed. A participant should be excluded if he/she has a positive test result for SARS-CoV2 infection, is known to have asymptomatic infection, or is suspected of having SARS-CoV2. Participants with active infections are excluded from study participation per Exclusion Criterion 19. When the infection resolves, the potential participant may be considered for re-screening. In addition, the following criteria apply:

- The participant must be able to perform all Screening and Day 1 procedures per the SoA (Section 1.3) at the study site (CXR, skin biopsy, SALT) and/or designated ancillary facility (eg, audiological evaluations and neurological evaluations) to determine whether the participant meets eligibility criteria for the study. This includes collection and resulting of laboratory assessments through the central laboratory vendor.
- The participant must meet eligibility criteria for the study and have had the initial Day 1 skin biopsy performed.
- At the time of Randomization it must be confirmed that the participant will be able to have the Month 1 and Month 3 safety laboratory tests collected/performed at the study site or an alternative clinical laboratory facility (including the participant's home, as available) according to the windows in Section 10.9.3.

If a participant does not meet the criteria described above, they cannot be enrolled in the study.

10.9.2. Telehealth Visits

In the event that in-clinic study visits cannot be conducted, every effort should be made to follow up on the safety of study participants at scheduled visits per the SoA (Section 1.3) or unplanned visits. Telehealth visits may be used to continue to assess participant safety and collect data points. Telehealth includes the exchange of healthcare information and services via telecommunication technologies (eg, audio, video, video-conferencing software) remotely, allowing the participant and the investigator to communicate on aspects of clinical care, including medical advice, reminders, education, and safety monitoring. The following assessments must be performed during a telehealth visit:

- Review dosing logs and record investigational product, including doses taken and any interruptions in intake of investigational product (ie, missed doses) since the last contact, and calculate compliance.
- Review and record any AEs and SAEs since the last contact. Refer to [Section 8.3](#).
- Review and record any new concomitant medications or changes in concomitant medications since the last contact.
- For WOCBP: Review and record contraceptive method and results of pregnancy testing. Confirm that the participant is adhering to the contraception method(s) required in the protocol. Refer to [Appendix 4](#) and [Section 10.9.3.1](#) of this appendix regarding pregnancy tests and to [Section 5.3.1](#) of this protocol regarding contraception checks.
- Body temperature and collection method (eg, oral, tympanic, axillary), pulse rate, and respiratory rate (measured by study participant/caregiver).
- Collection of interim audiological history (using Part 1 in the Audiometry Guide Worksheet for Post Day 1 visits) at visits requiring audiological evaluation with entry of clinically significant changes onto the AE section of the eCRF, as appropriate.
- Collection of interim neurological history (using General Neurology and Neuropathy Assessment Completion Guidelines) must be obtained, with entry of clinically significant changes onto the AE section of the eCRF, as appropriate.
- Administration of the C-SSRS performed by a qualified rater. As per [Section 8.2.11.1](#), if there are “yes” answers on items 4 or 5 of the suicidal ideation section or on any question in the suicidal behavior section of the C-SSRS, the participant will be discontinued from the study and referred to a mental health professional for appropriate evaluation and treatment.

NOTE: If the investigator determines that additional evaluation is warranted based on the information collected during the remote visit described above, follow-up is required to be performed, with results submitted to and reviewed by the investigator prior to shipping investigational product to the participant.

Study participants must be reminded to promptly notify site staff about any change in their health status.

The SALT and the PGI-C are not assessed if the visit is not onsite.

10.9.3. Alternative Facilities for Safety Assessments

10.9.3.1. Laboratory Testing (Usual Safety Assessments)

With the exceptions noted in Section 10.9.1 for Screening and Day 1, if a study participant is unable to visit the site for protocol-specified safety laboratory evaluations, testing may be conducted at a local laboratory if permitted by local regulations. The local laboratory may be a standalone institution or within a hospital. Collection of blood and urine samples may also be performed at the participant's home per Section 10.9.5.

The following safety laboratory evaluations may be performed at a local laboratory or in the participant's home:

- Hematology;
- Serum chemistry;
- Lipid panel (for visits on or before Month 15E);
- Urinalysis (for visits after Month 15E urinalysis will be performed only if considered clinically indicated by the investigator);
- Pregnancy testing (for WOCBP);
- Tuberculosis testing;
- Refer to the SoA (Section 1.3) for visits at which these tests are required and to Section 10.2 for additional details regarding these tests.

If it is not possible for the participant to have the above tests completed within the visit window specified in the SoA (Section 1.3), an extended window may be allowed to collect samples for these laboratory tests, provided that the investigator has performed the remote visit as described above, assessed each case, and determined that it would not increase risk to a participant. The extended windows for laboratory sample collection for each study visit are noted in Table 4. These windows apply only to laboratory samples collected during interruptions due to public emergencies, including the COVID-19 pandemic, based upon written notification from Pfizer. If the laboratory samples are not collected within the specified extended window for the visit, the participant must temporarily withhold investigational product until the required laboratory samples can be collected.

If a local laboratory is used, qualified study site personnel must order, receive, and review results. Site staff must collect the local laboratory reference ranges and certifications/ accreditations for filing at the site. Laboratory test results are to be provided to the site staff as soon as possible and must be received and reviewed by the investigator within 14 days after they are collected in order to determine eligibility to continue dosing. In addition, laboratory test results from the previous visit must be available and reviewed by the investigator prior to shipping investigational product at the current visit. The local laboratory reports should be filed in the participant's source documents/medical records. Relevant data from the local laboratory report should be recorded on the CRF.

Special attention should be paid to ensure that laboratory results are checked against the Guidelines for Participant Safety Monitoring and Discontinuations in Section 10.7 and that required follow-up is performed as applicable.

If a participant requiring pregnancy testing cannot visit a local laboratory for pregnancy testing, a home urine pregnancy testing kit with a sensitivity of at least 25 IU/mL may be used by the participant to perform the test at home, if compliant with local regulatory requirements. Urine pregnancy test results may be collected based on information provided by the participant (or their legally authorized representative, if appropriate) during the remote visit. **The urine pregnancy test result must be available prior to dispensing or shipping investigational product to a participant.** The pregnancy test outcome should be documented in the participant’s source documents/medical records and relevant data recorded on the CRF. It should be confirmed that the participant is adhering to the contraception method(s) required in the protocol.

Table 4. Windows for Remote Visits, Laboratory Sample Collections, and Special Safety Assessments if Required due to Public Emergencies Including COVID-19

Visit Identifier	Visit Month (Day in Study)	Remote Visit Window (Day in Study) ^a	Lab Collection Window (Day in Study) ^b	Special Safety Assessment Window (Day in Study) ^c
3	Month 1 (Day 31)	±3 days (Day 28-34)	-7/ +14 days (Day 24-45)	NA
4	Month 3 (Day 91)	±7 days (Day 84-98)	-14/ +30 days (Day 77-121)	NA
5	Month 6 (Day 181)	±7 days (Day 174-188)	-14/ +30 days (Day 167-211)	-14/+30 days (Day 167-211)
6	Month 9 (Day 271)	±7 days (Day 264-278)	-14/ +14 days (Day 257-285)	-14/ +60 days (Day 257-331) ^c
7	Month 3E (Day 91E)	±7 days (Day 84E-98E)	-14/ +30 days (Day 77E-121E)	NA
8	Month 6E (Day 181E)	±7 days (Day 174E-188E)	-14/ +30 days (Day 167E-211E)	NA
9	Month 9E (Day 271E)	±7 days (Day 264E-278E)	-14/ +30 days (Day 257E-301E)	-14/ +30 days (Day 257E-301E)
10	Month 12E (Day 361E)	±7 days (Day 354E-368E)	-14/ +30 days (Day 347E-391E)	NA
11	Month 15E (Day 451E)	±7 days (Day 444E-458E)	-14/ +30 days (Day 437E-481E)	-14/ +30 days (Day 437E-481E)
12	Month 21E (Day 631E)	±7 days (Day 624E-638E)	-14/ +30 days (Day 617E-661E)	NA
13	Month 27E (Day 811E)	±7 days (Day 804E-818E)	-14/ +30 days (Day 797E-841E)	-14/ +30 days (Day 797E-841E)
14	Month 33E (Day 991E)	±7 days (Day 984E-998E)	-14/ +30 days (Day 977E-1021E)	NA
15	Month 39E (Day 1171E)	±7 days (Day 1164E-1178E)	-14/ +30 days (Day 1157E-1201E)	-14/ +30 days (Day 1157E-1201E)
16	Month 45E (Day 1351E)	±7 days (Day 1344E-1358E)	-14/ +30 days (Day 1337E-1381E)	NA
17	Month 51E (Day 1531E)	±7 days (Day 1524E-1538E)	-14/ +30 days (Day 1517E-1561E)	-14/ +30 days (Day 1517E-1561E)

- a. These are the same as the windows in the protocol SoA (Section 1.3).
- b. Laboratory results must be received and reviewed by the investigator within 14 days after they are collected to determine eligibility to continue dosing. In addition, laboratory test results from the previous

Table 4. Windows for Remote Visits, Laboratory Sample Collections, and Special Safety Assessments if Required due to Public Emergencies Including COVID-19

Visit Identifier	Visit Month (Day in Study)	Remote Visit Window (Day in Study) ^a	Lab Collection Window (Day in Study) ^b	Special Safety Assessment Window (Day in Study) ^c
------------------	----------------------------	-------------------------------------------------	---------------------------------------------------	--------------------------------------------------------------

visit must be available and reviewed by the investigator prior to shipping investigational product at the current visit.

- c. The visit window for the on-site visit (Special Safety Assessments) for Month 9 is -7/+60 days and (Section 10.9.4). During TP3, the only special safety assessment is the audiological assessment.

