1.3. Schedule of Activities

1.3.1. Screening and Day 1

The Schedule of Activities (SoA) table provides an overview of the protocol visits and procedures. Refer to the Study Assessments and Procedures Section 8 of the protocol for detailed information on each procedure and assessment required for compliance with the protocol.

The investigator may schedule visits (unplanned visits) in addition to those listed in the SoA table, in order to conduct evaluations or assessments required to protect the well-being of the participant.

Some procedures conducted as part of the participant’s routine clinical management (eg, chest radiograph [CXR] or other appropriate diagnostic imaging such as computed tomography or magnetic resonance imaging [MRI]) and obtained before signing the informed consent document (ICD) may be utilized for screening or baseline purposes provided the procedures met the protocol-specified criteria and were performed within the time frame defined in the SoA.

Procedure	Screening	Day 1	Notes
Visit Identifier	1	2	Day 1 (Visit 2) is the last day of screening and the first day of the placebo-controlled phase for eligible participants.
Day	-35 to -1	1	
Visit Window (\pm Days)	None	None	
Enrollment procedures			
Informed consent	X		Must be obtained before the participant is enrolled in the study per Section 10.1.3 .
Inclusion and exclusion criteria	X	X	Pre-dose on Day 1. See Section 5.1 and Section 5.2 .
Demography	X		
Medical and AA disease history	X	X	Pre-dose on Day 1. Refer to the CRF completion guidelines for specific information regarding medical history information to be collected for each group of participants per Section 8.2.1 . Medical history includes neurological and audiological history per Section 8.2.5 and Section 8.2.6 .
Smoking, drug, and alcohol history	X		See Section 8.2.1 .
Medical procedures			
Full physical examination, including dermatological full body examination.	X	X	Pre-dose on Day 1. See Section 8.2.1 and Section 8.2.9.2 .
Neurological evaluation by a neurologist	X		The examination will include the Neuropathy Assessment. Refer to the Manuals for General Neurological and Neuropathy Assessments for more information. See Section 8.2.5 .
Audiological evaluation and history by an audiologist	X		Participants must have a full audiological assessment completed during screening prior to Day 1. Audiology and BAEP evaluations should be done on the same day, with

Procedure	Screening	Day 1	Notes

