Home Pregnancy Test Schedule (in addition to clinic visits)

Procedure	Intervention Period													
	TP1: Placebo-controlled Phase					TP2: Active Therapy Extension Phase								
Phase:														
Month	2	4	5	7	8	1E	2E	5E	7E	8E	10E	11E	13E	14E
Home pregnancy test	X	X	X	X	X	X	X	X	X	X	X	X	X	X

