8.2.13. Pregnancy Testing

Pregnancy tests may be urine or serum tests but must have a sensitivity of at least 25 mIU/mL. Pregnancy tests will be performed in WOCBP at the times listed in the SoA (Section 1.3). Following a negative pregnancy test result at screening, appropriate

contraception must be commenced, and a second negative pregnancy test result will be required at the baseline visit prior to the participant's receiving the study intervention.

In addition to pregnancy tests performed at the site, site personnel will instruct applicable participants to complete monthly urine pregnancy tests between study visits starting after the Month 1 visit through the Month 51E/EOT visit. The pregnancy testing between visits may occur outside of the study site. Urine pregnancy kits will be provided to participants at each study visit (starting at Month 1) and site personnel will instruct participants on when and how to administer the pregnancy test and how to interpret the result. The participants will be given enough kits to cover the monthly testing between visits (for example, at least 2 kits should be given at the Month 3 visit). Site personnel will be required to document the discussion, including confirmation of participant willingness to perform administered urine pregnancy test, and understanding of how to perform the test as well as how to interpret the test result. In addition, site personnel will contact participants between study visits to obtain monthly pregnancy test result and ensure this contact and the result of the pregnancy test are recorded in participant source documentation and the CRF.

Pregnancy tests will also be done whenever 1 menstrual cycle is missed during the active treatment period (or when potential pregnancy is otherwise suspected) and at the end of the study. Pregnancy tests may also be repeated if requested by institutional review boards (IRBs)/ethics committees (ECs) or if required by local regulations. If a urine test cannot be confirmed as negative (eg, an ambiguous result), a serum pregnancy test is required. In such cases, the participant must be excluded if the serum pregnancy result is positive. In the case of a positive confirmed pregnancy, the participant will be withdrawn from administration of study intervention but may remain in the study for follow-up.

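### Pregnancy-test passages conflict: the emergency appendix gives kit sensitivity in IU/mL where Section 8.2.13 uses mIU/mL, and the TP2 home-test table omits Month 4E

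*Protocol*

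**What the plan says.** Protocol Section 8.2.13 sets the general standard: "Pregnancy tests may be urine or serum tests but must have a sensitivity of at least 25 mIU/mL". It also has women of childbearing potential "complete monthly urine pregnancy tests between study visits starting after the Month 1 visit through the Month 51E/EOT visit". The pregnancy-test note in the Schedule of Activities (Section 1.3.2.1) gives the same monthly between-visit rule for TP1 and TP2, through Month 15E. Section 5.3.1 attaches a contraception check to the monthly phone contact at which the home result is obtained.

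Appendix 9 covers public emergencies. For a participant who cannot get to a local laboratory, Section 10.9.3.1 provides that "a home urine pregnancy testing kit with a sensitivity of at least 25 IU/mL may be used by the participant". The same paragraph adds: "The urine pregnancy test result must be available prior to dispensing or shipping investigational product to a participant".

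The home pregnancy test table that follows the TP1/TP2 Schedule of Activities marks Months 2, 4, 5, 7 and 8 in TP1, and Months 1E, 2E, 5E, 7E, 8E, 10E, 11E, 13E and 14E in TP2. Month 4E does not appear.

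On which text governs, Section 1.3.1 sends the reader to "Section 8 of the protocol for detailed information on each procedure and assessment required for compliance with the protocol", whereas Section 10.9 opens with "The alternative study measures described in this section are to be followed during public emergencies".

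**The concern.** Section 2.3.1 names routine pregnancy testing as part of the mitigation for potential fetal risk, so both passages belong to a safeguard the Protocol relies on.

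The emergency clause states a sensitivity that does not agree with the general rule, for a test whose result must be known before drug is released. The table is what a site would naturally use to book home tests and phone contacts. Followed as printed, it skips one test that the surrounding text requires, and the contraception check made at that contact could be skipped with it.

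The stake is operational and concerns participant safety. It does not touch the primary endpoint, the precision calculation or any planned summary.

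**Working it through.** There is no plan figure to reproduce. The check is a unit conversion and a comparison of required with listed months.

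**1. Sensitivity unit**
- Section 8.2.13: 25 mIU/mL, for urine or serum tests.
- Section 10.9.3.1: 25 IU/mL, for the emergency home kit.
- Conversion: 1 IU = 1000 mIU, so 25 IU/mL = 25 × 1000 = 25,000 mIU/mL.
- Ratio: 25,000 / 25 = 1000.

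A kit that meets 8.2.13 also meets 10.9.3.1. The reverse does not hold.

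**2. Where a site working from the appendix is sent**
- Section 10.9.2 (telehealth) refers to Appendix 4 and Section 10.9.3.1 for pregnancy tests, not to 8.2.13.
- Section 10.9.3.1 refers to Section 10.2 for test details. Section 10.2 cites 8.2.13 only for the screening criteria, and its own note on pregnancy tests gives no sensitivity.
- Section 10.9.6 (home health visits) cites both 8.2.13 and 10.9.3.1, so the reader meets both figures.

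**3. Between-visit months**
- TP1: Months 1 to 9 minus clinic visits {1, 3, 6, 9} = {2, 4, 5, 7, 8}. All 5 are listed.
- TP2: Months 1E to 15E minus clinic visits {3E, 6E, 9E, 12E, 15E} = {1E, 2E, 4E, 5E, 7E, 8E, 10E, 11E, 13E, 14E}, which is 10 months. The table lists 9, and the missing month is 4E.
- TP3: the footnote to the Section 1.3.2.2 schedule covers every between-visit month from 16E to 50E.
- The table has 14 month entries (5 + 9) and 14 X marks, so a single lost cell does not explain the gap. Month 4, the matching month in TP1, is listed.

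**4. Length of the gap if only the table is used**
- The Month 3E visit is Day 91E. With the schedule's 30-day months, 4E falls at about Day 121E and 5E at about Day 151E.
- From 3E to 5E: 151 − 91 = 60 days. With a 4E test: 121 − 91 = 30 days.

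**5. Reach of the emergency clause**
- Table 4 of Appendix 9 runs to Month 51E. Its TP3 rows are Visits 12 to 17 (21E, 27E, 33E, 39E, 45E, 51E), or 6 visits. This is an upper limit, because the clause applies only while emergency measures are in force.

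**6. Whether Month 4E is already past (an inference; no date is stated)**
- SAP version 4.0 (17 Aug 2022) speaks of analyses already added to the PCD CSR. Under Protocol Section 9.4.1 that report follows the lock of Month 9 data for all participants.
- Allow the full +60-day emergency window for Month 9: 17 Aug 2022 + 60 days = 16 Oct 2022. Add 120 days from Day 1E to Day 121E: 13 Feb 2023.
- That is 50 days before SAP version 5.0 (04 April 2023).

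**The case against.** The best counter-argument is that neither slip changes what the Protocol requires. Section 8.2.13 is general and mandatory, while the emergency clause is only permissive. A kit that satisfies the first satisfies the second, so no site has to choose between them. Home kits are supplied through the study under 8.2.13, and the documents describe no route to a much less sensitive one. Appendix 9 is confined to the COVID-19 pandemic, or to another emergency after written notice from the sponsor, and within that to participants who cannot reach a local laboratory. For Month 4E, the Schedule of Activities note, 5.3.1 and 8.2.13 all keep the monthly rule in force. Section 8.2.13 also gives at least 2 kits at Month 3 as an example, a visit with the same three-month spacing as 3E.

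Most of this stands, and it is why the point is minor. The 1000-fold ratio is a literal reading and not evidence that an insensitive kit would be used. The 60-day gap needs a site to rely on the table alone.

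The argument does not remove the contradictions. The appendix's cross-references do not reliably lead back to the general figure. Section 8.2.13 sizes kit supply to the months between visits, while the emergency clause does not say where its kit comes from. A schedule table that disagrees with the note in its own section is still an error in operative text.

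**Conclusion.** The concern holds, at minor severity. Both passages are wrong as written. Sections 10.9.3.1 and 8.2.13 differ by a factor of 1000 in stated sensitivity, and the TP2 home-test table gives 9 of the 10 months that the monthly rule requires.

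The conclusion on the unit assumes only that the printed text is operative. That the difference is a slip is likely from the shared number, but it is for the sponsor to confirm. The 60-day figure assumes nominal visit days and use of the table alone. If the dating inference is right, every participant has passed Month 4E and that half only corrects the record. The unit conflict can still matter at up to 6 TP3 visits if emergency measures apply. Sample size and the primary analysis are unaffected.

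**What to change.** Reconcile the sensitivity unit in Section 10.9.3.1 with Section 8.2.13, and add to the appendix a cross-reference to the passage that governs. Reconcile the TP2 home-test table in Section 1.3.2.1 with the monthly between-visit rule for Month 4E. Which statement is intended is for the sponsor to decide.

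The cost is two short wording edits, by clarification letter or in the next amendment, with no change to the SAP. The TP3 home-test footnote in Section 1.3.2.2 labels its months as belonging to the Observation Period. That label could be tidied in the same edit, although it is a separate matter.
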